### **Methodology:**

This is a double-blind, randomized, placebo-controlled study to evaluate the safety, tolerability, efficacy of adjunctive ganaxolone IV solution in subjects with SE. This study will start with a small open-label group to confirm that the dose selected will achieve a potentially therapeutic exposure (bolus plus continuous infusion) to stop SE. The dose selected for Day 2 is designed to provide a stable plasma concentration to maintain status cessation. If needed, doses in the open-label group portion of the study may be adjusted based on the dosing and pharmacokinetic/safety profile from the subject's enrolled.

As previously described, the study drug will be added to the standard of care from the time that the first 2nd line IV AED, administered at an appropriate dose and duration to show efficacy, has failed and the second 2nd line IV AED is medically indicated during the treatment of SE. Study drug must be administered with the 2nd line IV AED treatment and should be initiated as close to the initiation of the second 2nd line IV AED as possible.

Potential subjects are anticipated to be identified in the emergency department and/or hospital in-patient or intensive care units.

Upon identification, subjects will be administered consent/assent and then screened for inclusion/exclusion criteria prior to receiving study drug as adjunctive therapy via continuous IV infusion, followed by a 12-hour study drug taper. As soon as the study drug administration is completed (with or without taper), subjects will have a 24-hour in-patient follow-up day and then follow-up visits/contacts at weeks 2, 3, and 4. For subjects who have the 12-hour study drug taper, the in-patient follow-up day starts as soon as the 12-hour study drug taper is complete. If the infusion rate becomes too low to sustain the infusion line, it can be discontinued at that point and the subject will progress into the in-patient follow-up day. For subjects where there is no study drug taper the in-patient follow-up day starts as soon as the study drug administration is discontinued. These subjects will continue with the week 2, 3, and 4 follow-up visits.

If the subject remains hospitalized, the week 2, 3, and 4 visits will be done in-person. If the subject has been discharged, these visits may be conducted via telephone call. However, it is recommended

that discharged subjects return so at least one of these visits will be conducted in-person. In total, each subject will be followed for approximately 4 weeks after the initiation of study drug.

### **Screening**

Procedures specific to this protocol will not be performed until written informed consent/assent from the subject/parent/guardian/legally authorized representative (LAR) has been appropriately obtained per the investigator's hospital policy. As many of the subjects will not be able to provide consent/assent, the parent/guardian/LAR will provide consent on behalf of the subject to participate in the study. As soon as the subject is able, per the investigator's hospitals guidelines, consent/assent will be administered to them for continued participation. Consent/assent for subjects who are known to be at risk for SE may be obtained prior to an SE event.

### **Treatment and Follow-up**

#### **Study Drug Dosing**

Up to approximately 30 subjects will be enrolled into the open-label group with ganaxolone and up to approximately 242 subjects will be randomized into the double-blind group. Subjects in the double-blind group will be randomized (1:1) to receive either ganaxolone IV solution or placebo with concurrent standard of care treatment. Study drug will be given as a bolus plus continuous infusion.

After study drug initiation, the standard duration of treatment is 2 days which includes a 12-hour study drug taper.

### **Safety and Assessments**

Study drug will be given in addition to standard of care for SE and medical or surgical interventions deemed appropriate by the investigator. In addition to the medically indicated treatment, safety and tolerability will be monitored by but not limited to the following:

1. Physical examinations should be completed at:
  - a. Pre-dose (screening) or, if not available, within 2 hours of study drug initiation, and at 36-hours (+/- 1-hour),
  - b. Time of study drug discontinuation, either at the end of the study drug taper or if the study drug is stopped without a taper and
  - c. 24-hours (+/- 1-hour) after study drug discontinuation.
  - d. If possible, for subjects who early terminate, collect at the time early termination is being considered and as close as possible to the end of the study drug administration.
  - e. Any time, if medically indicated, per investigator's judgment.
2. Status Epilepticus Severity Score (STESS) should be collected pre-dose (screening).
3. Vitals and the Glasgow Coma Scale (GCS) or Pediatric Glasgow Coma Scale (PGCS), Richmond Agitation and Sedation Scale (RASS), and the Full Outline of UnResponsiveness (FOUR) Score scales should be collected at:
  - a. Pre-dose (screening), 60-minutes (+/- 15-min), 2- (+/- 15-min), 10-, 24-, and 36-hours (+/- 1 hour) after study drug initiation,
  - b. Time of study drug discontinuation, either at the end of the study drug taper or if the study drug administration is stopped without a taper and
  - c. 24-hours (+/- 1-hour) after study drug discontinuation.
  - d. If possible, for subjects who early terminate from the study, collect at the time early termination is being considered and as close as possible to the end of the study drug administration.

e. Any time, if medically indicated, per investigator's judgment.

Weight and height should be collected pre-dose (screening) for calculation of the BMI inclusion criterion, if feasible. If not collected pre-dose (screening), collect prior to the end of the in-patient follow-up day.

4. Mini Mental State Examination (MMSE) should be performed at:
  - a. The time consent/assent is administered to the subject for continued participation and then on the in-patient follow-up day.

If the MMSE is not able to be assessed due to the subject's state, this should be recorded.

  5. Electrocardiogram (ECG), the subject should have an ECG at:
    - a. Pre-dose (screening), 2- (+/- 30-min) and 36-hours (+/- 1-hour) after study drug initiation,
    - b. Time of study drug discontinuation; either at the end of the study drug taper or if the study drug administration is stopped without a taper and
    - c. 24-hours (+/- 1-hour) after study drug discontinuation.
    - d. If possible, for subjects who early terminate from the study, collect at the time early discontinuation is being considered and as close as possible to the end of the study drug administration.
    - e. Any time, if medically indicated, per investigator's judgment.
  6. Clinical laboratory measures, hematology, serum chemistry (including creatinine, blood urea nitrogen, and estimated glomerular filtration rate calculation), and concomitant AED levels (fosphenytoin/phenytoin, valproic acid, levetiracetam, lacosamide, or brivaracetam, if available), and Urinalysis (including urine protein, albumin and microscopic), should be collected at:
    - a. Pre-dose (screening), if available, or within 2 hours of study drug initiation, at 24- and 36-hours (+/- 1-hour) after study drug initiation,
    - b. Time of study drug discontinuation, either at the end of the study drug taper or if the study drug administration is stopped without a taper and
    - c. 24-hours (+/- 1-hour) after study drug discontinuation.
    - d. One of the weekly follow-up visits (week 2, 3, or 4) for subjects in-house and if possible, for subjects who have been discharged.
    - e. If possible, for subjects who early terminate from the study, collect at the time early termination is being considered and as close as possible to the end of the study drug administration.

Variable collections based on subject response:

- f. After the initial SE cessation, AED levels should be collected at time of first instance of seizure activity or SE relapse.

Between study drug initiation and the in-patient follow-up day, where possible, collect a sample:

- i. If the decision is made to intubate the subject
- ii. At the time of a serious adverse event (related or not related)
- g. Any time, if medically indicated, per investigator's judgment.

7. Drugs of abuse (urine or serum), including alcohol testing and Pregnancy test (urine or serum) for women who are of childbearing potential, should be collected pre-dose (screening). If not possible to collect pre-dose, collect as soon as possible after start of study drug infusion. Enrollment is not contingent upon results. However, if a subject has a positive test result, it will be at the investigator's discretion to weigh the risks versus benefits for the

subject's continued participation. If the investigator decides to discontinue the study drug, refer to the study drug taper directions in the Study drug, Dose, and Mode of Administration section.

8. EEG is required for confirmation of non-convulsive status epilepticus (NCSE) diagnosis. Ideally, continuous EEG monitoring should start before study drug initiation and continue through the in-patient follow-up day. If continuous EEG is not possible or needed to diagnose (for convulsive SE) it should be instituted at the earliest possible time after study drug initiation (if a pre-dose EEG was not performed for the diagnosis of convulsive SE). Several study sites may be offered the use of a rapid EEG device to assist with pre-screening of subjects with NCSE. It will be at the investigator's discretion if they feel the device will benefit their site. More details can be found in Section 7.2.2.

9. Blood sampling for pharmacokinetic analysis (venous or arterial) of ganaxolone will be collected at the following times:

Required collections:

- After the start of the study drug infusion: 60-minutes, then 2-, 4-, 8-, 10-, 24- and 36-hours,
- At the time of study drug discontinuation, either at the end of the study drug taper or if the study drug administration is stopped without a taper and
- 24-hours after study drug discontinuation.

Variable collections based on subject response:

- After the initial SE cessation, collect a sample at the first instance of seizure activity or SE relapse and the subject does not progress to an IV anesthetic drug (a 3rd line treatment, e.g. midazolam, propofol, thiopental, pentobarbital, or ketamine)

Between study drug initiation and the in-patient follow-up day, where possible, collect a sample:

- If the decision is made to intubate the subject
- At the time of introduction of a new IV AED for safety/efficacy (not for AEDs given prophylactically for "transition/bridging")
- At the time of any serious adverse event (related or not related)

If study drug is administered via central access, the PK sample must not be collected from any central access ports. If study drug is administered via venous access, the PK sample must be collected via the contra-lateral arm of the study drug arm. The location of study drug access and location of PK sample collection should be documented in the subject's source. If the PK sample cannot be collected due to poor venous access and the study drug infusion site is the only viable option, the specimen should not be collected and the reason for non-collection documented in the subject's source.

10. Blood sampling for neurosteroid levels (venous or arterial) will be collected pre-dose (screening) and at 24-hours (+/- 1-hour) of study drug initiation. If study drug is discontinued during this 24 hours, the second sample should be collected prior to study drug discontinuation, if possible.

The same collection rules as noted for pharmacokinetic sample collection apply for the neurosteroid sample collection.

11. Blood gas including  $\text{FiO}_2$ ,  $\text{PaO}_2$ , and arterial pH, if collected per the investigator's discretion for subject's care, from the time of SE diagnosis through the of the in-patient follow-up day and recorded in the eCRF. If samples are not collected, a sample is not required.

However, if the decision is made to intubate the subject from study drug initiation through the end of the in-patient follow-up day, a blood gas sample should be collected. The sample should be collected immediately prior to or as close as possible to the time of intubation. During the study, it is expected that the total blood volume drawn from subjects for all safety, pharmacokinetic, and neurosteroid sampling at pediatric-only hospitals is approximately 62 to 88 mL of blood and at all other hospitals approximately 192.6 to 278.3 mL of blood, regardless of sex.

12. Cerebral Spinal fluid sample collection: If a subject has a lumbar puncture for the collection of cerebral spinal fluid (CSF) per investigator's discretion as part of their care and there is adequate volume, a sample will be aliquoted for future analysis of ganaxolone. If multiple lumbar punctures are performed, a sample from each puncture is requested. However, if not collected or not enough CSF is available to provide a sample for the study, a sample is not required.

13. Clinical Global Impression of Severity and Improvement (CGI-S and CGI-I, respectively)  
CGI-S is collected at:

- a. Pre-dose (screening) and 36-hours (+/- 1-hour) after study drug initiation,
- b. Time of study drug discontinuation, either at the end of the study drug taper or if the study drug administration is stopped without a taper and
- c. 24-hours (+/- 1-hour) after study drug discontinuation.
- d. Week 2, 3, and 4 follow-up visits (in-person or via telephone call).
- e. If possible, for subjects who early terminate from the study, collect at the time early termination is being considered and as close as possible to the end of the study drug administration.
- f. Any time, if medically indicated, per investigator's judgment.

CGI-I is collected at:

- a. Within the first 2 hours of study drug initiation and 36-hours (+/- 1-hour) after study drug initiation,
- b. Time of study drug discontinuation, either at the end of the study drug taper or if the study drug administration is stopped without a taper and
- c. 24-hours (+/- 1-hour) after study drug discontinuation.
- d. Week 2, 3, and 4 follow-up visits (in-person or via telephone call).
- e. If possible, for subjects who early terminate from the study, collect at the time early termination is being considered and as close as possible to the end of the study drug administration.
- f. Any time, if medically indicated, per investigator's judgment.

14. Modified Rankin Scale (MRS) should be collected at:

- a. Time of study drug discontinuation, either at the end of the study drug taper or if the study drug administration is stopped without a taper and
- b. 24-hours (+/- 1-hour) after study drug discontinuation.
- c. Week 2, 3 and 4 follow-up visits (in-person or via telephone call).
- d. If possible, for subject's who early terminate from the study, collect at the time early termination is being considered and as close as possible to the end of the study drug administration.
- e. Any time, if medically indicated, per investigator's judgment.

15. Status Epilepticus and Seizure Questions should be collected at:

- a. 15-minutes (+/- 5-min), 30-, 60-minutes (+/- 15-min), 2-, 4-, 6-, 8-, 10-, 12-, 18- (+/- 30-min), and 24- and 36-hours (+/- 1 hour) after study drug initiation,
- b. Time of study drug discontinuation, either at the end of the study drug taper or if the study drug administration is stopped without a taper and
- c. 24-hours (+/- 1-hour) after study drug discontinuation.
- d. Week 2, 3, and 4 follow-up visits (in-person or via telephone call).
- e. If possible, for subjects who early terminate from the study, collect at the time early termination is being considered and as close as possible to the end of the study drug administration.

Assessment questions:

1. Is the subject in SE currently?
2. Was the subject in SE since the previous assessment?  
(Note: N/A for the 15-minute timepoint)
3. Is the subject having seizures currently?
4. Did the subject have seizures since the previous assessment?  
(Note: N/A for the 15-minute timepoint)
5. Have any new\* AEDs been initiated since the last assessment?  
(Note: “New” refers to any AED that has not already been used to treat the current episode of SE)
6. If a new AED was initiated, was it to treat the current seizure/SE episode or initiated prophylactically (e.g., for transition/bridging), or other reason?  
(Note: “Prophylactic” refers to any elective/transitional/bridging AED therapy that is not indicated to treat seizure/EEG abnormal activity at this time or since the last assessment)

Record any new AEDS on the concomitant eCRF page.

16. Intubation Question will be collected for subjects who are intubated either prior to study drug initiation or anytime through the end of the in-patient follow-up day:

- a. 18- (+/- 30-min), 24-, and 36-hours (+/- 1 hour) after study drug initiation,
- b. Time of study drug discontinuation, either at the end of the study drug taper or if the study drug administration is stopped without a taper and
- c. 24-hours (+/- 1-hour) after study drug discontinuation.

Assessment point:

1. Per your evaluation has the subject’s medical condition improved enough to warrant considering extubation?

17. Adverse events (AEs) and Concomitant medications: AE’s will be collected throughout the study via non-direct questioning. Concomitant medications will be collected during the same time period however, the collection requirements will differ depending on the subject’s treatment progression as defined below.

- a. All adverse events and associated concomitant medications will be collected through the in-patient follow-up day.
- b. IV anesthetic agents (midazolam, propofol, thiopental, pentobarbital, or ketamine) administered during the study drug treatment period and the in-patient follow-up day should be followed through the week 4 visit/contact.
- c. During the weekly follow-up visits, only ongoing AEs and new AEs assessed by the investigator to be related to study drug will be recorded and the concomitant medications associated with these AEs.

- d. In addition, during the weekly follow-up visits, AEs of urinary tract infection (UTI), hospital-acquired/ventilator-associated pneumonia, myocardial infarction (MI), sepsis from any source, critical illness myopathy/neuropathy, significant hypotension requiring support of vasopressors will be recorded regardless of relatedness. Associated concomitant medications for these AEs will not be recorded.
- e. All SAEs regardless of relationship to study drug and their associated concomitant medications will be recorded from the time of study drug initiation through the last follow-up visit/contact.
- f. For subjects who early terminate from the study, prior to discontinuation as much information as is available should be recorded for ongoing AEs/SAEs, new AEs/SAEs and their associated concomitant medications, especially those that may have led to the early termination.

For some of the concomitant medications only the highest dose administered will be required in the eCRF. Reference the eCRF Completion Guidelines for guidance.

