Added guidance regarding dose adjustments and interruptions and that the Marinus Medical Monitor must approve re-start of infusion for interruptions > 6 hours		Synopsis and Section 6.2.3
As there is no longer an option to extend the study drug treatment for four days, removed reference to EEG seizure burden calculation		Synopsis and Section 7.2.2.1
Updated the required and variable collection timepoints for safety and efficacy assessments/procedures; added Modified Ranking Scale (MRS), Full Outline of UnResponsiveness (FOUR) Scale and Intubation Question; added 2 questions to the Seizure and SE		Synopsis, Table 1, and Sections 7.2.2.1, 7.2.2.2, 7.2.2.3, 7.2.2.4, 7.2.2.5, 7.2.2.6,

Questionnaire. Removed collection timepoints from specific assessment/procedure text in Section 7	7.2.2.7, 7.2.3.3, 7.2.3.4, 7.2.3.6, 7.2.3.7, 7.2.3.8
Expanded collection requirements for Blood Gas	Synopsis, Table 1 footnote n, and Section 7.2.3.5
Added guidance on the collection locations for the pharmacokinetic and neurosteroid samples	Synopsis, Table 1 footnotes l and m, and Section 7.2.4.1, Table 4 and 5
Added collection requirements for cerebral spinal fluid, if a lumbar puncture is performed per investigator's discretion as part of their care, and if there is adequate volume for future analysis of ganaxolone	Synopsis, Table 1 footnote o, and Section 7.2.4.3.1, 9.9
Listed examples of IV anesthetics including ketamine	Synopsis, Table 1 footnote u, and Sections 4.2, 5.2, 5.2.2, 7.1.3
Added that "a 4 th line treatment", "a 4 th line treatment e.g., immunosuppressants, magnesium" is prohibited	Synopsis and Sections 5.2.2, 6.2.3, 7.1.3
Modified when AEs and concomitant medications will be collected and added specific AEs that need to be recorded during the weekly follow-up visits.	Synopsis, Table 1, and Sections 5.2, 8.1,
Modified exclusion criterion #8 to exclude subjects who are currently on dialysis but allow subjects to start dialysis during the study	Synopsis and Sections 4.2, 4.5.1
Modified secondary endpoints for level of responsiveness to include the Four Score Scale and RASS; for clinical outcome the Modified Ranking Scale will be used; for hospital metrics including length of stay, need for and duration of intubation and mechanical ventilation.	Synopsis and Sections 2.2, 9.7.2
Table 1 Visit/Timepoint or Duration updated to support revised study design; footnotes updated to support revised required and variable collection timepoints	Table 1

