u. AEs and concomitant medications will be collected throughout the study; non-direct questioning will occur. The collection requirements will differ depending on the subject's treatment progression as follows: 1. All adverse events and associated concomitant medications will be collected through the in-patient follow-up day. 2. IV anesthetic agents (midazolam, propofol, thiopental, pentobarbital, or ketamine) administered during the study drug treatment period and the in-patient follow-up day should be followed through the week 4 visit/contact. 3. During the weekly follow-up visits, only ongoing AEs and new AEs assessed by the investigator to be related to study drug will be recorded and the concomitant medications associated with these AEs. 4. In addition, during the weekly follow-up visits, AEs of urinary tract infection (UTI), hospital-acquired/ventilator-associated pneumonia, myocardial infarction (MI), sepsis from any source, critical illness myopathy/neuropathy, significant hypotension requiring support of vasopressors will be recorded regardless of relatedness. Associated concomitant medications for these AEs will not be recorded. 5. All SAEs regardless of relationship to study drug and their associated concomitant medications will be recorded from the time of 1st dose through the last follow-up visit/contact. 6. For subjects who early terminate from the study, prior to discontinuation as much information as is available should be recorded for ongoing AEs/SAEs, new AEs/SAEs and their associated concomitant medications, especially those that may have led to the early termination.

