Potential subjects must have failed one 2nd line IV AED therapy, administered at an appropriate dose and duration to show efficacy. Ganaxolone IV solution (open-label group) or ganaxolone IV solution or placebo (double-blind group) will be administered in combination with standard of care at the time that the first 2nd line IV AED has failed and the second 2nd line AED is medically indicated during the treatment of SE. Study drug must be administered with 2nd line IV AED treatment and should be initiated as close to the dose initiation of the second 2nd line IV AED as possible.

Upon administration of study drug, subjects will be monitored for improvement or resolution of SE (clinical or EEG response).

Note, the infusion rate cannot be rounded-up regardless whether dosing is in subjects  $\geq 40$  kg or  $< 40$  kg.

Subjects weighing at least 40 kg:

- A 30-mg bolus dose (over ~3 minutes) will be administered with a continuous infusion of 80 mg/hour for 2 hours followed by a continuous infusion rate of 40 mg/hour for 10 hours, and then 20 mg/hour for the remaining 12 hours of Day 1.
- On Day 2 (24-36 hours) the continuous infusion rate of 20 mg/hour will continue until the start of the study drug taper at 36 hours post study drug initiation. If needed, to manage seizure relapse or another medical reason, the infusion rate can be increased from 20 mg/hour up to a maximum rate of 45 mg/hour at any time during hours 24-36 of Day 2.
- To taper the study drug, the infusion rate at the 36-hour post study drug initiation timepoint will be reduced by 33.3% every 4 hours until the infusion is stopped or if the infusion rate becomes too low to sustain the infusion line, at which point it will be stopped. The first taper will be 33.3% from the current infusion rate, the second taper will be 33.3% from the first tapered infusion rate, and the final taper will be 33.3% from the previous tapered infusion rate. If, per the investigator's judgment, the study drug taper needs to start at an earlier timepoint during the treatment period, the infusion rate at the start of the first taper will be decreased by 33.3% every 4 hours as described.
- At the time the study drug infusion is discontinued the subject will progress to the in-patient follow-up day assessments/procedures.

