### Scenarios for stopping the study drug without a taper include:

- For subjects who receive study drug for less than 2 hours and/or
- Study drug infusion is discontinued or interrupted, and the decision is made to not restart the infusion and/or
- If at any time during study drug administration the subject progresses to an IV anesthetic drug (a 3rd line and/or 4th line treatment) for seizure suppression or
- It is no longer safe to continue drug administration per the investigator’s medical judgment.

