#### **7.2.3.3 Adverse Event Collection**

Subjects and their parent/guardian/LAR will be questioned in a general way to ascertain if AEs have occurred (e.g., "Have you had any health problems since your last visit?"). Adverse events are collected from the time of first dose of study drug through the last follow-up visit/contact.

Refer to Section 8, Adverse and Serious Adverse Events Assessment.

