## 8. ADVERSE AND SERIOUS ADVERSE EVENTS ASSESSMENT

### 8.1 Definition of Adverse Events, Period of Observation, Recording of Adverse Events

An AE is any untoward medical occurrence in a clinical investigation subject who has been administered a pharmaceutical product; it does not necessarily have a causal relationship with this treatment. An AE can therefore be any unfavorable and unintended sign (including an abnormal laboratory finding), symptom, or disease temporally associated with the use of a medicinal (investigational) product, whether or not related to the medicinal (investigational) product.

As this study allows for pre-consenting of subjects, all AEs will be collected from the time of first dose of study drug until the defined follow-up period stated in Section 7.1.3. Where possible, a diagnosis rather than a list of symptoms should be recorded. If a diagnosis has not been made, then each symptom should be listed individually. All AEs should be recorded on the appropriate AE pages in the eCRF and in source documents. In addition to untoward AEs, unexpected benefits outside the study drug indication should also be recorded on the AE eCRF page.

All AEs must be followed for the durations described below. For AEs followed to closure, this indicates that an outcome is reached, stabilization is achieved (the investigator does not expect any further improvement or worsening of the event), or the event is otherwise explained. When appropriate, medical tests and examinations are performed so that resolution of event(s) can be documented.

For subjects who:

- a. Have 2 days of treatment which includes a 12-hour study drug taper, all adverse events will be collected through the in-patient follow-up day. During the weekly follow-up visits only, ongoing AEs and new AEs assessed by the investigator to be related to study drug will be recorded. All SAEs regardless of relationship to study drug will be recorded from the time of 1st dose through the last follow-up visit/contact.

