- b. Stop study drug administration without a study drug taper but continue with the follow-up visits, all adverse events will be collected through the in-patient follow-up day. During the weekly follow-up visits, only ongoing AEs and new AEs assessed by the investigator to be related to study drug will be recorded. All SAEs regardless of relationship to study drug will be recorded from the time of 1st dose through the last follow-up visit/contact. Additionally, AEs of UTI, hospital-acquired/ventilator-associated pneumonia, MI, sepsis from any source, critical illness myopathy/neuropathy and significant hypotension requiring vasopressor support will be recorded as AEs regardless of relatedness.
- c. Early terminate from the study, prior to discontinuation as much information as is available should be recorded on any on-going AEs/SAEs and AEs/SAEs that may have led to the early termination.

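### Six named late adverse events are recorded in all subjects by the protocol synopsis and Table 1 but only after a stop without taper by section 8.1, and SAP 4.9.1 tabulates relatedness without saying that late recording was filtered on it

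*Protocol*

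**What the plan says.** **Protocol, Amendment 4.** Synopsis item 17c sets the rule for the weekly contacts: "only ongoing AEs and new AEs assessed by the investigator to be related to study drug will be recorded". Item 17d adds six terms: urinary tract infection, hospital-acquired or ventilator-associated pneumonia, myocardial infarction, sepsis, critical illness myopathy or neuropathy, and hypotension needing vasopressors. Item 4 of Table 1 footnote u repeats the list, ending "significant hypotension requiring support of vasopressors will be recorded regardless of relatedness". Neither place limits it to a subgroup. The summary of changes dates it to Amendment 4: "added specific AEs that need to be recorded during the weekly follow-up visits".

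Section 8.1 divides subjects by how treatment ended. Item (a), for those with the full two days including the taper, says "During the weekly follow-up visits only, ongoing AEs and new AEs assessed by the investigator to be related to study drug will be recorded" and has no list. Item (b), for those who stop without a taper, has the same filter and then the list: "critical illness myopathy/neuropathy and significant hypotension requiring vasopressor support will be recorded as AEs regardless of relatedness". Serious events are recorded through the last contact under both items.

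Section 6.2.3 gives the grounds for stopping without a taper. One is: "If at any time during study drug administration the subject progresses to an IV anesthetic drug". The same section lets the investigator decide that "the study drug taper needs to start at an earlier timepoint during the treatment period".

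**SAP, written to Amendment 3.** Section 4.9.1 treats every event from first dose to the end of follow-up as treatment-emergent and summarises these events by severity and relationship. Appendix 1 footnote v states the collection rule: at the weekly visits, ongoing events, new related events and all serious events. It has no list, and 4.9.1 does not refer to it.

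**The concern.** Two separate matters arise, under two protocol versions.

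First, Amendment 4 gives sites two rules for the same contact. A taper completer with a new, non-serious urinary tract infection in Week 3 that is judged unrelated is recorded under the synopsis and Table 1, but not under section 8.1(a). A subject who escalated to an IV anesthetic and has the same infection is recorded under both. Escalation within 24 hours is also failure of the primary endpoint, so under 8.1 the ascertainment of a safety outcome depends on an efficacy outcome. That would be an undesirable feature in any comparison between arms.

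Second, a table by relationship is informative only if related and unrelated events had the same chance of being recorded. For new non-serious events after the in-patient follow-up day they did not, and SAP 4.9.1 gives the reader of the table no sign of this.

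**Working it through.** The first point rests on reading the rules against one another. The second needs only a short argument about direction. The plan gives no figure to reproduce.

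**1. Who gets the six-term list at the weekly contacts**

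| Subject | Synopsis 17d and Table 1 footnote u(4) | Section 8.1 | SAP Appendix 1 footnote v (Amendment 3) |
|---|---|---|---|
| Completes two days with taper | List applies | (a): no list | No list |
| Stops without taper | List applies | (b): list applies | No list |
| Taper started early | List applies | Neither (a) nor (b) | No list |

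Amendment 3 had one filter with or without a taper. The conflict came in with the list.

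**2. Which events are at risk.** Serious events and events already ongoing are recorded under every version. Myocardial infarction, sepsis and vasopressor-dependent hypotension would usually meet the serious criteria in section 8.2.3. What can be lost in taper completers is mainly urinary tract infection and milder pneumonia or myopathy/neuropathy. The division between serious and non-serious is a clinical judgement; the documents give no counts.

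**3. Whether analysed subjects are affected.** Amendment 4's Day 1 dose at 40 kg or more (section 6.2.3, Table 2) is 30 + (80 × 2) + (40 × 10) + (20 × 12) = 30 + 160 + 400 + 240 = 830 mg. SAP section 1 defines cohorts with targets of 713, 650 and 500 mg/day. The summaries of earlier amendments give about 714 mg/day for Amendment 3 and about 500 mg/day for Amendment 2. No cohort is at 830. This is not proof, since infusion parameters could be changed by administrative memo, but it suggests that few or no analysed subjects were treated under the Amendment 4 wording.

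**4. How much of the SAP's event window is filtered.** On the Amendment 3 schedule in SAP Appendix 1, full recording covers dosing, the 18-hour taper and the 24-hour in-patient day:

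- shortest: 48 + 18 + 24 = 90 h = 3.75 days; filtered share 21 / (3.75 + 21) = 21 / 24.75 = 85%
- longest: 96 + 18 + 24 = 138 h = 5.75 days; filtered share 21 / (5.75 + 21) = 21 / 26.75 = 79%

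These are shares of calendar time on the nominal schedule. They are not shares of events, which need not occur evenly over time.

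**5. Direction of the error in the by-relationship table.** Let R be the number of related events, N the true number of unrelated events, and M the number of unrelated, new, non-serious late events not recorded. Then:

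- true related share = R / (R + N)
- tabulated related share = R / (R + N − M)

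The second exceeds the first whenever R and M are both above zero. The documents give no value for M. The error lies in the related share of all events. The percentage of subjects with a related event, which SAP 4.4 bases on all subjects in the group, is not inflated by this route.

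**The case against.** The best case on the other side has four parts.

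- **Nobody analysed may be affected by the section 8.1 conflict.** The SAP cohorts point to earlier amendments. This stands, and it limits the first point mainly to what is carried into the phase 3 study.
- **The comparison that would suffer is not made here.** The SAP covers only the open-label group and has no inferential test. A reader might infer that section 8.1 would give the arm with fewer escalations a calculable false safety advantage. The documents do not support a figure: it would need the true incidence in escalated and non-escalated subjects and the proportion of sites following 8.1. Section 1.1 also says that third-line agents usually lead to coma, intubation and ventilation, so these complications may well be commoner after escalation, and part of any recorded difference would be real. The dependence on outcome remains; its size is unknown.
- **The protocol says elsewhere how to collect events.** Section 7.1.3 sends sites to Table 1 for follow-up assessments, and Table 1 has the list for everyone. That helps, but section 8.1 is the section on recording adverse events and says otherwise. A reader might also take section 7.2.3.3 ("Adverse events are collected from the time of first dose of study drug through the last follow-up visit/contact") as a third, unfiltered rule. It is not: the next line refers to Section 8.
- **The SAP discloses the filter.** Footnote v states it, all events are listed, and no early-versus-late comparison is planned. This makes the second point small. It does not remove it, because the tables in 4.9.1 carry no reference to the footnote.

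**Conclusion.** Both points hold, and both are minor.

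The Amendment 4 conflict is plain in the text. Under section 8.1, capture of the non-serious listed events would follow outcome, because escalation to an IV anesthetic leads to stopping without a taper. The loss is confined to new, non-serious, unrelated listed events in subjects outside 8.1(b). Its effect on the subjects analysed under this SAP may be nil.

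The SAP point concerns the only data the SAP analyses. The related share of treatment-emergent events is overstated if any unrelated, new, non-serious event began after the in-patient day. It would be tempting to attach a percentage. That would require the proportion of such events that start late and the proportion judged unrelated, and the documents give neither. Nor can a general loss of late safety data be inferred, since serious and ongoing events were recorded throughout.

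**What to change.** **Protocol section 8.1, and the phase 3 protocol.** Replace the separate weekly-visit rules in (a) and (b) with one rule for every subject who enters the weekly visits, whether after a full taper, an early taper or none. It should cover ongoing events, new related events, the six named terms regardless of relatedness, and all serious events.

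**SAP 4.9.1.** Either tabulate treatment-emergent events with onset through the in-patient follow-up day (the post-taper day in the SAP's terms) separately from later ones, or footnote the tables. Suggested footnote: *New non-serious AEs with onset after the in-patient follow-up day were recorded only if judged related or, where the protocol version in force had one, on the named list.*

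**Cost.** One paragraph in section 8.1 and one table split or footnote, with no new visit or test. The protocol change brings a few extra event entries in taper completers, many of which will be complications of critical illness. For open-label subjects already followed up, only the SAP change can still help.
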